# 2.0 STATISTICAL HYPOTHESES

The primary focus of the study is to offer continued guadecitabine treatment to subjects who are benefiting from the treatment and to collect the safety information of guadecitabine. No formal statistical hypotheses will be tested in the analysis of the trial data. All analyses will be descriptive in nature.

## **3.0 SAMPLE SIZE DETERMINATION**

The sample size for this extension study was based on the eligible subjects from prior guadecitabine studies. No formal sample size justification was necessary.

#### 4.0 ANALYSIS SETS

For purposes of analysis, the following analysis sets are defined:

Analysis Set	Description
All Subjects	All screened subjects, including those who did not meet the study entry criteria or did not receive a study treatment.
Safety	All subjects who receive any amount of study treatment.
Efficacy	All subjects who receive any amount of study treatment.

### 5.0 STATISTICAL ANALYSES

### 5.1 General Considerations

No formal statistical hypotheses will be tested. All analyses will be descriptive in nature.

Continuous variables will be summarized with mean, standard deviation, median, minimum, and maximum. Categorical variables will be summarized with counts and percentages. The SAS® statistical package (version 9.4 or a later version) will be used for the analyses.

Summary tables of efficacy, and safety data will be provided.

Summaries of disposition will be based on the All Subjects analysis set (all screened subjects). Demographics and baseline characteristics, as well as efficacy summaries will be based on the Efficacy analysis set. Safety summaries will be based on the Safety analysis set. In this study, the Safety and Efficacy analysis sets are identically defined.

Unless otherwise specified, the baseline value is defined as the last value collected prior to initiation of the study treatment in the SGI-110-12 study. For variables which are collected on Day 1 of Cycle 1 (C1D1) without explicit timing, the C1D1 values will be used as the baseline values.

Month is defined as 30.4375 days for analyses conducted in this study.

Study day of an SGI-110-12 subject is defined in reference to the subject's C1D1 date in SGI-110-12 and calculated following the data programming standards as detailed in BDM Manual 02 - Astex Data Programming Standards.

Laboratory values recorded as an interval such as " $\geq x$ ", "< x", or "2+" or recorded as below the limit of quantification (BLQ) will be handled, if necessary, for calculation purposes, following the data programming standards as detailed in BDM Manual 02 - Astex Data Programming Standards.

Incomplete medication and AE start and stop dates will be imputed conservatively following the data programming standards as detailed in BDM Manual 02 - Astex Data Programming Standards.

# 5.2 **Participant Dispositions**

The number and percentage (n, %) of subjects screened, enrolled (by prior study), treated, treatment discontinuation (with reason) and withdrawn from study (with reason) will be summarized. All screened subjects will be included in the disposition analysis.

# 5.3 **Primary Endpoint(s) Analysis**

The primary endpoint is safety as measured by adverse events. Please refer to Section 5.5.2 Adverse Events for the detail analyses.

### 5.4 Secondary Endpoint Analysis

# 5.4.1 Key/Confirmatory Secondary Endpoint

Long-term overall survival is a secondary endpoint. Survival duration for each subject starting from the time of randomization in the prior study will be determined.

### 5.4.1.1 **Definition of Endpoint(s)**

Overall Survival (OS)

Overall survival is defined as time, in days, from the time of randomization in the prior study to the date of death (regardless of cause). Subjects without a documented death date at the time of analysis will be censored at the last date known alive.

Survival time in days = (earliest of date of death or censoring – randomization date in the prior study)

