2.0 RATIONALE

2.1 Rationale for the Study

While mortality is the most common outcome for patients with the conditions being treated in guadecitabine clinical studies, a small proportion of subjects survive to the end of the study and continue to receive treatment with guadecitabine at the time of database close. Of the 401 subjects treated in the first guadecitabine clinical study (SGI-110-01), 8 subjects continue to receive guadecitabine treatment, with a treatment duration (as of November 2017) of 2.8 to 5.6 years

(34-68 cycles). Phase 3 Study SGI-110-04 will close in 2018 and it is expected that there will be subjects still benefitting from guadecitabine treatment at the time that study closes. Rather than have each clinical study remain open to allow continued guadecitabine treatment, this extension study will provide one protocol under which subjects who have benefitted from guadecitabine treatment may continue to receive guadecitabine.

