5.2 Inclusion Criteria

To be eligible for the study, subjects must fulfill all of the following inclusion criteria:

- Previous participation in an Astex-sponsored guadecitabine clinical trial (including but not limited to SGI-110-01, SGI-110-04, SGI-110-05, SGI-110-06, and SGI-110-07), in which the subject was treated with guadecitabine and was still on active treatment with guadecitabine at the time of database close for the prior study.
- Subject is considered to be benefitting from guadecitabine treatment in the opinion of the treating investigator.
- Able to understand and comply with the study procedures, understand the risks involved in the study, and provide written informed consent before any study-specific procedure.
- 4. Women of child-bearing potential (according to recommendations of the Clinical Trial Facilitation Group [CTFG]; see below* for details) must not be pregnant or breastfeeding and must have a negative pregnancy test at screening. Women of child-bearing potential and men with female partners of child-bearing potential must agree to practice 2 highly effective contraceptive measures while receiving treatment with guadecitabine and for at least 3 months after completing treatment and must agree not to become pregnant or father a child while receiving study treatment and for at least 3 months after completing guadecitabine treatment. Contraceptive measures which may be considered highly effective comprise combined hormonal contraception (oral, vaginal, or transdermal) or progestogen-only hormonal contraception (oral, injectable, implantable) associated with inhibition of ovulation, intrauterine device, intrauterine hormone-releasing system, bilateral tubal occlusion, sexual abstinence, and surgically successful vasectomy. Abstinence is acceptable only if it is consistent with the preferred and usual lifestyle of the subject. Periodic abstinence (eg, calendar, ovulation, symptothermal, or postovulation methods) and withdrawal are not acceptable methods of birth control.

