### 5.4.1.2 Main Analytical Approach

The OS curves will be estimated using the Kaplan-Meier method (Kaplan et al 1958). The median (and quartiles) duration of OS and the associated 95% CI (based on the log-log transformation for the survival function) will also be generated.

In addition, OS curves will also be estimated using the Kaplan-Meier method by the disease types (treatment-naive AML, relapse/refractory AML, and relapse/refractory intermediate- or high-risk MDS (including CMML). The median (and quartiles) duration of OS and the associated 95% CI (based on the log-log transformation for the survival function) will be generated for each group of the disease types.

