### 6.2 Appendix 2: Changes to Protocol-planned Analyses

Overall survival definition is changed from

"Time, in days, from the time of the **first dose of Guadecitabine** in the prior study to the date of death"

to

"Time, in days, from the time of **randomization** in the prior study to the date of death".

All subjects enrolled in the SGI-110-12 study were from the prior studies involving randomization. These prior studies used the randomization date as the start date for overall survival. The change of the SGI-110-12 start time of the overall survival from the first dose of Guadecitabine to the date of randomization is to maintain the definition consistence between SGI-110-12 and the prior randomized studies.

In addition, overall survival analysis by disease types is added.

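### Overall survival is counted from prior-study randomization, but only in subjects who had to survive to the extension, so ordinary Kaplan-Meier overstates it

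*SAP*

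**What the plan says.** **Time origin.** SAP 5.4.1.1: "Overall survival is defined as time, in days, from the time of randomization in the prior study to the date of death". The formula there subtracts only the prior-study randomization date from the date of death or censoring. It has no term for entry into SGI-110-12.

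**Who is analysed.** SAP 5.1 bases efficacy summaries on the Efficacy set, defined in SAP 4.0 as: "All subjects who receive any amount of study treatment". That means dosed in the extension. Protocol 5.2 admits a subject only if he or she "was still on active treatment with guadecitabine at the time of database close for the prior study", and adds: "Subject is considered to be benefitting from guadecitabine treatment in the opinion of the treating investigator".

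**Estimator.** SAP 5.4.1.2 specifies Kaplan-Meier curves with median, quartiles and 95% confidence intervals, overall and by disease type. Neither document mentions left truncation, delayed entry, a landmark or a caution on interpretation.

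**Stated reason.** SAP Appendix 2 (6.2) changes the origin from first guadecitabine dose to randomization because "These prior studies used the randomization date as the start date for overall survival". Protocol 11.6 had used first dose in the prior study, said only that each subject's survival duration may be determined, and specified no Kaplan-Meier analysis.

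**The concern.** The clock starts at randomization, but a subject becomes observable for this analysis only at the first SGI-110-12 dose. Anyone who died in between is absent from the data set, so the interval is immortal time. Ordinary Kaplan-Meier places every extension subject in the risk set from day 0 and divides the later deaths by risk sets that include people who could not yet have been seen to die.

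The curve therefore stays at 100% up to the shortest randomization-to-entry gap. Beyond that, its level depends heavily on how long the prior studies ran before closing. The disease-type curves have the same defect, and they can differ from one another merely because the feeder studies had different gaps.

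Survival is the study's only efficacy outcome (Protocol 11.6), and SAP 5.4.1 places it under a key/confirmatory heading. A reader who takes up the consistency argument of Appendix 2 and sets these medians beside prior-study results would see very long survival even if the drug did nothing.

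**Working it through.** The documents give no survival figure, event target or power for this endpoint, so there is no planned number to reproduce. Three checks were made.

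**1. From the documents alone.** Protocol 2.1 reports that 8 of 401 subjects treated in SGI-110-01 were still on guadecitabine, "with a treatment duration (as of November 2017) of 2.8 to 5.6 years". That is 8/401 = 2.0%. The lower end is 2.8 × 12 = 33.6 months. A survival curve for those 8 could not fall before about 33.6 months, whatever happened to the other 393. This shows the mechanism; no analysis of those 8 alone is planned.

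**2. Scaled to the protocol's own survivor count.** Protocol 4.2 gives about 1600 Phase 3 subjects and an upper bound of 326 on treatment at close if all survivors were guadecitabine subjects. This implies S = 326/1600 = 0.204 alive at close. Assume exponential survival with true median m, the same follow-up F for all, and all survivors entering.
- Follow-up at close: F = m × log2(1/0.204) = 2.30m.
- Planned median: the time by which half of those alive at F have died, F + m = 3.30m.

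Simulation (1,000,000 subjects per scenario) also let follow-up at close vary uniformly, with a maximum-to-minimum ratio of 1, 2 or 3, scaled to keep 20.4% alive:

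| True median (months) | Planned Kaplan-Meier median | Median from extension entry |
|---|---|---|
| 6 | 19.6–19.8 | 6.0 |
| 9 | 29.3–29.7 | 8.9–9.0 |
| 12 | 39.1–39.5 | 12.0 |

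The ratio is 3.25 to 3.30 in all nine scenarios. At the shortest follow-up time the planned curve reads 100% where true survival is 20% to 43%.

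**3. A different closure pattern.** Assume exponential survival, S(t) = 2^(−t/m), and closure uniform between 18 and 36 months after randomization. The fraction entering is D = (1/18)∫S(f)df over 18 to 36. For t in that range the planned curve is K(t) = [((t−18)/18)·S(t) + (1/18)∫S(f)df over t to 36] / D. For t above 36 it is S(t)/D.

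For m = 12: D = 0.220. K(24) = [(6/18) × 0.25 + 0.120]/0.220 = 0.926, against a true 0.25. The median solves S(t) = 0.110, so t = 12 × log2(1/0.110) = 38.2 months.

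| True median (months) | Planned median | Planned 24-month survival | True 24-month survival |
|---|---|---|---|
| 8 | 33.7 | 88% | 12.5% |
| 12 | 38.2 | 93% | 25% |
| 18 | 44.5 | 95% | 40% |

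Simulating this setting with 42 months of extension follow-up gave the same medians. Delayed-entry Kaplan-Meier gave survival to 24 months, conditional on being alive at 18, of 0.60, 0.72 and 0.80, against true values of 0.595, 0.707 and 0.794.

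**Sensitivity to constant hazard.** With gamma frailty of variance 1, S(t) = 1/(1 + t/m). At 20.4% alive, F = m(1/S − 1) = 3.91m and the planned median is m(2/S − 1) = 8.82m. The residual median from entry is 8.82m − 3.91m = 4.91m. So part of the excess is selection of good-prognosis subjects, which changing the origin does not remove.

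**The case against.** The best defence is that survival here is secondary and descriptive. The primary endpoint is adverse events, no hypothesis is tested, there is no control arm, and no comparison with prior-study survival is planned. Total survival since randomization among those who reached the extension is a quantity that can be computed, and on this view only a label is missing.

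The facts are right, but they do not rescue the analysis. The SAP never describes the curve as conditional. The stated objective concerns subjects who participated in a previous guadecitabine study, a wider group, and Appendix 2 ties the definition to studies that impose no such survival condition. A descriptive median can still be badly misleading.

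Three narrower objections stand in part:
- The magnitudes depend on assumed hazards, closure times and follow-up. They illustrate the bias and do not forecast the result.
- The agreement between the median from entry and the true median holds only under constant hazard, as the frailty case shows.
- The per-subject survival duration in Protocol 11.6 is not itself biased. Its origin also precedes entry, but the bias arises once such an origin is combined with the SAP's ordinary Kaplan-Meier.

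**Conclusion.** The concern holds. That the planned curves, medians and quartiles overstate survival relative to the randomized population follows from the eligibility rule, the analysis set, the time origin and the estimator, with no outside assumption.

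The size is conditional. It is about 3.3-fold on the median with exponential survival, 20.4% alive at close and all survivors entering, and 8.8-fold with strong frailty, where selection contributes as well as immortal time. None of these calculations models the on-treatment and benefitting criteria.

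Changing the origin or using delayed entry removes the immortal time only. Neither recovers survival in the randomized population, because the subjects remain selected for benefit. The point needs correcting even though the endpoint is descriptive, since it affects the study's only efficacy output.

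**What to change.** In SAP 5.4.1 to 5.4.1.2 and Appendix 2:

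1. Make the main survival analysis time from SGI-110-12 Cycle 1 Day 1 to death, overall and by disease type, and call it residual survival.
2. If a curve on the randomization time scale is still wanted, estimate it by left-truncated Kaplan-Meier with each subject entering the risk set at Cycle 1 Day 1. Label it conditional on being alive, on treatment and enrolled. Show numbers at risk, because early risk sets may be small, especially by disease type.
3. Remove the randomization-origin median and quartiles from ordinary Kaplan-Meier.
4. State that the results are not comparable with overall survival in the prior studies, and replace the consistency argument in Appendix 2.

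The cost is SAP wording and a few lines of code. Both dates are already needed: SAP 5.1 uses Cycle 1 Day 1 as the reference for study day. The reported survival times will be shorter. Follow-up that ends at the safety visit, about 30 days after the last dose, is a separate source of possible bias that this change does not address.

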Subjects will attend the clinic for treatment with guadecitabine on Days 1-5 of each 28-day cycle. When treatment is permanently discontinued, follow-up will stop with the safety follow-up visit occurring 30 ± 7 days after the last guadecitabine treatment or when an alternative anticancer treatment is administered, whichever occurs first. Adverse events and concomitant medications will be collected throughout the study. Samples for limited hematology and serum chemistry assessments will be collected at screening, Day 1 of each cycle, and at the safety follow-up visit. For women of childbearing potential, a pregnancy test will be performed at screening and on Day 1 of each cycle prior to treatment. Survival status will be recorded when the subject is withdrawn from the study. Other clinical assessments may be performed as part of standard of care but the performance and results of these assessments will not be collected for this study.

Sample Size and Statistical Analyses:

There is no sample size requirement for this extension study. Summaries of treatment exposure and adverse events may be provided. The timing of such analyses will depend on the needs of the clinical development program.

Study Duration and Termination:

The study is expected to start in Q2 2018. The study may continue as long as subjects are receiving treatment with guadecitabine, or until guadecitabine becomes commercially available (anticipated for Q4 of 2019).

Compliance Statement:

The study will be conducted in accordance with the International Council for Harmonisation (ICH) Good Clinical Practice (GCP) guidelines, principles enunciated in the Declaration of Helsinki; and all human clinical research regulations in countries where the study is conducted.

TABLE OF CONTENTS

| PRO | TOCO | L APPRO | OVAL PAGE | 3 |
|-----|-------|----------|--|----|
| ABB | REVIA | ATIONS A | AND DEFINITIONS | 10 |
| 1.0 | INT | RODUCT | TON AND BACKGROUND | 11 |
| | 1.1 | Guadec | citabine Mechanism of Action | 11 |
| | 1.2 | Nonclin | nical Data on Guadecitabine | 12 |
| | 1.3 | Clinical | 1 Data and Human Pharmacokinetics | 12 |
| | 1.4 | Potentia | al Risks and Benefits to Human Subjects | 13 |
| 2.0 | RAT | | 2 | |
| | 2.1 | Rationa | ale for the Study | 13 |
| | 2.2 | Rationa | ale for Guadecitabine Dose and Regimen | 14 |
| 3.0 | STU | DY OBJE | ECTIVES | 14 |
| | 3.1 | Primary | y Objective | 14 |
| | 3.2 | Second | ary Objective(s) | 14 |
| 4.0 | INV | ESTIGAT | ΓΙΟΝΑL PLAN | 14 |

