9.0 STUDY ASSESSMENTS AND PROCEDURES

9.1 Efficacy Assessments

There are no efficacy assessments in this study, except for survival status which will be documented at the time of withdrawal from the study.

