10.3 Reporting Requirements for Serious Adverse Events (SAEs)

All SAEs regardless of causality will be reported by the investigator to Astex Pharmaceuticals through the 30-day period after the last dose of study treatment. Deaths and SAEs occurring after the 30-day safety follow-up period AND considered related to study treatment or study procedures must also be reported.

Report all SAEs (initial and follow-up information) on an SAE form and send the form to Astex Pharmaceuticals Drug Safety, or designee, within 24 hours of the discovery of the event or information (see below). Astex Pharmaceuticals may request follow-up and other additional information from the investigator (eg, hospital admission or discharge notes, laboratory results).

| Astex Pharmaceuticals Drug Safety Contact Information | | | | | | |
|---|-------------------|--|--|--|--|--|
| Telepho | Telephone Numbers | | | | | |
| Local Number: | | | | | | |
| North America Toll Free | | | | | | |
| Fax Numbers | | | | | | |
| Local Fax: | | | | | | |
| Toll Free Fax | | | | | | |
| Email | | | | | | |
| Drug Safety Inbox | | | | | | |
| Other countries: Refer to the Astex Fax Cover Sheet for the Drug Safety Department. All safety fax numbers are listed there. | | | | | | |

Report all deaths with the primary cause of death as the SAE term, as death is the outcome of the event, not the event itself. If an autopsy was performed, report the primary cause of death on the autopsy report as the SAE term. Forward autopsy and postmortem reports to Astex Pharmaceuticals Drug Safety, or designee, as outlined above.

If study treatment is discontinued, temporarily suspended, or dose reduced because of an SAE, include this information in the SAE report.

Suspected Unexpected Serious Adverse Reactions (SUSARs) are SAEs that qualify for mandatory expedited reporting to regulatory authorities where the SAE is suspected to be caused by the study treatment and is considered unexpected (ie, not defined as expected in the current IB clinical study protocol, or approved labeling for marketed drugs). In this case, Astex Pharmaceuticals Drug Safety or designee will report to the relevant regulatory authorities and forward a formal notification describing the SUSAR to investigators, according to regulatory requirements. Each investigator must then notify his or her IRB/IEC of the SUSAR as required by local regulatory authorities and in accordance with IRB/IEC policy.

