11.9 Procedures for Handling Missing, Unused, and Spurious Data

No imputation of values for missing data will be performed. Data from subjects lost to follow-up will be included in statistical analyses to the point of their last evaluation.

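### Overall survival is defined as all-cause, but after a subject leaves the study deaths are captured unevenly and by cause, so the Kaplan-Meier curve does not estimate all-cause survival and its bias could go either way

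*SAP*

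**What the plan says.** **Endpoint and censoring.** SAP 5.4.1.1 runs overall survival (OS) from randomization in the prior study "to the date of death (regardless of cause"). On censoring it says: "Subjects without a documented death date at the time of analysis will be censored at the last date known alive". Survival time ends at the "earliest of date of death or censoring". SAP 5.4.1.2 then asks for Kaplan-Meier curves, medians and quartiles, overall and by disease type.

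**Collection of survival status.** The Protocol Synopsis (Study Assessments and Procedures) states: "Survival status will be recorded when the subject is withdrawn from the study". Protocol 9.1 agrees, naming "survival status which will be documented at the time of withdrawal from the study" as the only efficacy assessment. Under Protocol 4.1 a subject who stops treatment has a safety visit 30 ± 7 days after the last dose, or before alternative anticancer therapy if that is sooner, and is then withdrawn. No survival contact is scheduled after that.

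**Death reporting.** Through 30 days after the last dose, Protocol 10.3 is broad: "All SAEs regardless of causality will be reported by the investigator". After that it narrows: "Deaths and SAEs occurring after the 30-day safety follow-up period AND considered related to study treatment or study procedures must also be reported".

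**Loss to follow-up.** Protocol 11.9 says: "Data from subjects lost to follow-up will be included in statistical analyses to the point of their last evaluation". SAP Appendix 2 changes the start of the OS clock and adds curves by disease type, but does not say how follow-up ends.

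**The concern.** Kaplan-Meier needs the length of follow-up to be unrelated to the outcome. Here, whether a leaver contributes time after exit depends on whether that subject died and whether the death became known. A leaver alive two years after exit normally contributes none of those two years. A leaver whose late death is reported contributes all the time up to death, and then an event. The late deaths that sites must report are also selected by a causality judgement, so the all-cause definition is not met after the 30-day window.

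OS is the only secondary endpoint, and SAP 5.4.1 places it under a Key/Confirmatory heading. Leavers accumulate with time, so the distortion is greatest in the late part of the curve, which is the part a long-term survival objective is about.

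**Working it through.** The documents give no OS figure, event count, exit rate or post-exit mortality, so there is no planned figure to reproduce. The check is whether the rule can recover a known survival curve.

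**Inputs, all assumed except where noted**
- Death hazard on study λ = 0.3 per year; after exit h = HR × λ, with HR from 1 to 3. Protocol 5.4.1 lists disease progression and toxicity among the exit reasons, so HR above 1 is plausible, but no value is given.
- Treatment stops at rate μ = 0.5 or 1.0 per year, with exit 30 days later (0.082 y).
- Analysis at C = 3.5 years, roughly the span from the planned Q2 2018 start to the SAP approval of 3 November 2021.
- A share p of post-exit deaths is documented and counted on the date of death. All other leavers are censored at exit.
- Clock from extension entry, for simplicity. The SAP clock starts earlier, so these are not the percentages the SAP would print.

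**Formulas**, with u = t − 0.082
- Still on study: B(t) = exp(−λt − μu).
- Left and alive: A(t) = μ·exp(−0.082λ)·exp(−hu)·[1 − exp(−ku)]/k, where k = μ + λ − h.
- True survival: B + A. True hazard: (λB + hA)/(B + A).
- Risk set under the SAP rule: R = B + pA·[1 − exp(−h(C − t))], because a leaver remains in it only if a documented death is still to come.
- Hazard seen by Kaplan-Meier: (λB + phA)/R, accumulated over time to give the curve.

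**One point by hand: t = 3, μ = 0.5, p = 10%**
- HR 1: B = 0.0945, A = 0.3120. R = 0.0945 + 0.1 × 0.3120 × 0.1393 = 0.0989. Deaths = 0.3 × 0.0945 + 0.1 × 0.3 × 0.3120 = 0.0377. Estimated hazard 0.0377/0.0989 = 0.38 against a true 0.30: too high.
- HR 2: B = 0.0945, A = 0.1873. R = 0.0945 + 0.1 × 0.1873 × 0.2592 = 0.0994. Deaths = 0.0284 + 0.1 × 0.6 × 0.1873 = 0.0396. Estimated hazard 0.40 against a true 0.50: too low.

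**Kaplan-Meier minus true 3-year survival, in points (μ = 0.5 / 1.0)**

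| HR after exit | True survival, % | p = 0 | p = 10% | p = 25% |
|---|---|---|---|---|
| 1 | 40.7 / 40.7 | 0 / 0 | −2.8 / −9.0 | −6.2 / −15.8 |
| 1.5 | 33.4 / 30.5 | +7.2 / +10.2 | +3.6 / −0.6 | −0.6 / −8.0 |
| 2 | 28.2 / 23.3 | +12.5 / +17.4 | +8.3 / +5.6 | +3.6 / −2.4 |
| 3 | 21.4 / 14.4 | +19.2 / +26.3 | +14.4 / +13.4 | +8.9 / +4.5 |

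**Reading the table.** Across each row, documenting more late deaths while giving surviving leavers no further time lowers the curve: this is the counting rule's own effect. Down each column, faster death among leavers censored at exit raises the curve relative to the truth. The two act together, and the sign of the net error depends on inputs that the documents do not give. The p = 0 column is what results if every later death is simply discarded: it is right only when HR = 1.

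**The case against.** **A reader might infer that the curve is biased downward.** The equal-hazard row supports that, but the documents do not say that leavers die at the same rate as stayers. If leavers die faster, the net error is often upward. Only the narrower statement stands: the counting rule lowers the curve relative to uniform censoring.

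**A reader might see a contradiction in the survival-time formula.** There is none. SAP 5.4.1.1 gives a censoring date only to subjects without a documented death, so the earlier of the two dates is the death date whenever one is documented.

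**Protocol 10.3 sets a reporting minimum.** Protocol 5.4.2 stresses follow-up information on subjects withdrawn prematurely, so other deaths may become known. The SAP also censors at the last date known alive, which can be later than the exit visit. Both points stand. They make late ascertainment uneven rather than strictly limited to related deaths, but without a scheduled contact they do not make it complete. The restriction also begins 30 days after the last dose rather than at exit, so someone leaving earlier for other therapy remains covered for serious events of any cause until then.

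**The analysis is descriptive.** SAP 2.0 tests no hypothesis, so no decision error follows. This limits the severity, but a descriptive OS curve should still estimate OS.

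**Conclusion.** The point holds in this form: after the 30-day window, ascertainment of death is incomplete and depends on outcome and cause, so the planned curve, median and quartiles are not a valid all-cause OS estimate. This follows from the text alone.

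The size and sign do not. In the illustration the 3-year error at p = 10% ranges from −9.0 to +14.4 points over HR 1 to 3. These figures rest on assumed constant hazards, exit rates and documentation shares, and on a clock started at extension entry. They show that the error can be material and can go either way; they do not predict the trial's result. For a descriptive secondary endpoint, the change should be made, but the primary safety analysis does not depend on it.

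**What to change.** **Preferred.** In SAP 5.4.1.1, set one common study-close date. Obtain vital status (alive or dead, with date) as of that date for every treated subject, including all who have left. Count every death up to that date as an event, whatever its cause, and censor all others at that date, or at last contact if earlier. With complete status this removes both the asymmetry and the selection by cause, at any post-exit hazard. The cost is one vital-status check per leaver, limited by what each subject's consent allows.

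**If that is not feasible.** Apply one end-of-follow-up rule alike to deaths and survivors: the end of the window in which deaths of any cause are captured (30 days after the last dose under Protocol 10.3), or study close for those still on treatment. Label the result on-study survival, not OS. List later deaths with cause. Add a sensitivity analysis that counts all documented deaths and varies post-exit mortality. The cost is a few sentences, one listing and one sensitivity analysis. The price in interpretation is higher: if leavers die faster, this estimate overstates all-cause survival, as the p = 0 column shows.

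The survival-time formula needs no change.
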